#### *PK Assessment:*

- A Pharmacokinetic (PK) assessment will be conducted in a sub-set of subjects to assess the amount of B2A in blood (plasma) after surgery, on Days 1, 2, 4, 7, and 15, and will include a baseline, pre-procedure evaluation. The sub-set of subjects will include up to

approximately 30 AMPLEX subjects, allowing pharmacokinetic evaluation in at least 20 AMPLEX subjects. Both genders will be represented. Blood samples will be collected and processed to plasma for laboratory evaluation (plasma B2A concentration).

#### **6.1.4 Surgical procedure**

In addition to the below text, further detail on surgical procedure can be found in the Surgical Manual.

The operative site will be prepared and draped for surgery using standard technique. The arthrodesis site will be prepared by decorticating any remaining arthritic cartilage down to subchondral bone. High speed mechanical instruments such as burrs are avoided to prevent excessive heat at the fusion site that may be detrimental to the biological processes required for fusion. The graft material should be packed in the joint space to minimize the chance of extrusion. Stable fixation of joint in the appropriate position is achieved using 1 to 3 internal fixation screws with or without supplemental fixation. Wound closure is performed using standard technique. A dressing is applied and the ankle and hindfoot are immobilized with a cast, splint or boot.

##### *Internal Fixation:*

Screws will be used for internal fixation in order to standardize the hardware. All fusion constructs should be comprised of at least one but not more than 3 screws. Supplemental pins and staples may be used. Supplemental screws and plates external to the fusion site(s) are also allowed. The manufacturers of the screws provide Instructions for Use and Surgical Technique for their respective products. These documents must be consulted for guidance on the use of instruments for surgical preparation, sizing of screws, and placement of the screws.

##### *Preparation of Graft Material:*

Graft material will be prepared during surgery using either autogenous bone or the AMPLEX material assigned through randomization. Graft materials are to be placed ONLY within the joint space.

- *AMPLEX, Investigational Treatment.* AMPLEX should be prepared following the IFU accompanying the kit. If the subject is assigned to receive AMPLEX, the lyophilized B2A powder will be reconstituted in sterile WFI and mixed with the granules at the time of surgery as per the IFU. Once reconstituted and mixed with granules, implant-ready AMPLEX must be used within four hours.
- *Autogenous Bone Graft, Control Treatment.* The harvested bone (calcaneus, proximal tibia, distal tibia, iliac crest, etc.) will be cleaned of soft tissue and morselized. The volume of ABG harvested for treatment should be measured using a syringe.

- The aggregate volume of AMPLEX or ABG utilized in index joints will be at the discretion of the surgeon, provided the joint space(s) can be adequately filled with graft material according to the following parameters:
  - Single hindfoot joint fusion: up to 5 cm^3
  - Double or triple hindfoot fusion: each individual joint up to 5 cm^3, but overall, not more than 10 cm^3 for the full complement of joints
  - Ankle fusion: up to 10 cm^3

### 6.1.5 Post-Operative Care

While in the hospital, subjects should be encouraged to mobilize out of bed by the first post-operative day. Physical therapy for ambulation and activities of daily living should also be provided per standard of care. The following will be performed prior to subject's release from the hospital or within 1 week following the procedure:

- Collect A/P, lateral and oblique X-rays of the hindfoot/ankle after implant

Hospital discharge will occur in accordance with the institutions' standard of care. Discharge instructions will include prescriptions for pain management. Sites should provide standard-of-care prophylaxis for thromboembolic disease and this may include ASA up to 325 mg bid. With the exception of ASA up to 325 mg bid for either cardiovascular protection and/or DVT prophylaxis, subjects will be instructed to avoid non-steroidal anti-inflammatory drugs (NSAIDs) and corticosteroids for the first 6 weeks following surgery. Subjects will be advised that the use of NSAIDs or systemic steroid therapy (not including topical steroid therapy) may interfere with bone healing. This also applies to limited use of NSAIDs for headache, dysmenorrhea, etc. Electromagnetic, ultrasound or osteobiologic treatments stimulating bone growth are not allowed. Subjects will be instructed to remain non weight-bearing for six (6) weeks, then allowed to progressively increase weight-bearing. During the progressively increased weight-bearing timeframe, a removable cast/splint or boot is worn, which is subsequently weaned after full weight-bearing is achieved. It is recommended that all subjects are directed to participate in a post-operative rehabilitation program consistent with the guidelines provided in [Table 2](#). Subjects will be advised against the use of tobacco products for at least six (6) months after surgery. Tobacco products will be defined as all tobacco products (cigarettes [including e-cigarettes], cigars, and chewing tobacco) and will include gum or patches that contain nicotine. Subjects will be advised that nicotine may increase the chances of wound infection, pseudarthrosis (nonunion) and other complications.

**Table 2 Post-operative Rehabilitation Guidance**

Phase	Average Time Post-surgery	Immobilization	Examples of phase appropriate activities
Phase 1	0-2 weeks	
 
• Rigid immobilization (e.g., cast)
 
	
 
• Gentle A/PROM of uninvolved joints (e.g., toes, knee, hip)
 
• Limb elevation
 
• Crutch/ambulatory aide instruction for strict NWB
 

Phase 2	2-6 weeks	
 
• Rigid immobilization (e.g., cast, walking boot)
 
	
 
• Continued NWB instruction
 

Phase 3	6-12 weeks	
 
• Rigid or flexible immobilization (e.g., walking boot, ankle brace)
 
	
 
• Progressive WB to tolerance
 

Phase 4	12-24 weeks	
 
• Flexible immobilization as needed (e.g., ankle brace)
 
	
 
• Physical Therapy rehabilitation program
 

### 6.1.6 Follow-up Visit at 2 Weeks

The visit window is  $\pm$  3 days.

- Physical assessment of hindfoot/ankle, including vital signs
- Collect two blood samples for: 1) non-fasting chemistry and 2) hematology. Additional details for the collection and handling of blood samples are provided in the SRM
- Subject-based Assessment:
  - If subjects are in the ABG group, ask subjects to rate their graft site pain on the VAS
- Record adverse events
- Record concomitant medications

### 6.1.7 Follow-up Visit at 6 Weeks

The visit window is  $\pm$  14 days.

- Physical assessment of hindfoot/ankle, including vital signs
- Collect three blood samples for: 1) non-fasting chemistry, 2) hematology and 3) immunogenicity testing for B2A antibodies. Additional details for the collection and handling of blood samples are provided in the SRM
- Subject-based Assessment:
  - If subjects are in the ABG group, ask subjects to rate their graft site pain on the VAS

- Collect A/P, lateral and oblique X-rays of the hindfoot/ankle
- Record adverse events
- Record concomitant medications

#### **6.1.8 Follow-up Visit at 12 Weeks**

The visit window is  $\pm$  14 days.

- Physical assessment of hindfoot/ankle, including vital signs
- Collect three blood samples for: 1) non-fasting chemistry, 2) hematology and 3) immunogenicity testing for B2A antibodies. Additional details for the collection and handling of blood samples are provided in the SRM
- If immune testing is positive, the subject will be reevaluated at each subsequent follow-up visit until the response is resolved or to the end of the study
- Collect A/P, lateral and oblique X-rays of the hindfoot/ankle
- Perform a CT scan of the hindfoot/ankle
- Subject-based Assessment:
  - Review the instructions for and ask the subject to complete the FAAM-ADL Questionnaire and weight-bearing pain VAS
  - If subjects are in the ABG group, ask subjects to rate their graft site pain on the VAS
- Record adverse events
- Record concomitant medications

#### **6.1.9 Follow-up Visit at 24 Weeks**

The visit window is  $\pm$  30 days:

- Physical assessment of hindfoot/ankle, including vital signs
- Collect A/P, lateral and oblique X-rays of the hindfoot/ankle
- Perform a CT scan of the hindfoot/ankle
- Subject-based Assessment:
  - Review the instructions for and ask the subject to complete the FAAM-ADL Questionnaire and weight-bearing pain VAS
  - If subjects are in the ABG group, ask subjects to rate their graft site pain on the VAS
  - Review the instructions for and ask the subject to complete the SF-12 Questionnaire
- Record adverse events
- Record concomitant medications

#### **6.1.10 Follow-up Visit at 52 Weeks**

The visit window is  $\pm$  30 days:

- Physical assessment of hindfoot/ankle, including vital signs
- Collect A/P, lateral and oblique X-rays of the hindfoot/ankle
- Perform a CT scan of the hindfoot/ankle
- Subject-based Assessment:
  - Review the instructions for and ask the subject to complete the FAAM-ADL Questionnaire and weight-bearing pain VAS
  - If subjects are in the ABG group, ask subjects to rate their graft site pain on the VAS
  - Review the instructions for and ask the subject to complete the SF-12 Questionnaire
- Record adverse events
- Record concomitant medications

#### **6.1.11 Follow-up Visit at 78 Weeks**

The visit window is  $\pm$  30 days:

- Physical assessment of hindfoot/ankle, including vital signs
- Collect A/P, lateral and oblique X-rays of the hindfoot/ankle
- Record adverse events
- Record concomitant medications

## 6.2 Trial Flow Chart

[figure not shown]

Figure 2 Trial Flow Chart

## 7 TRIAL ASSESSMENTS

### 7.1 Schedule of Assessments

**Table 3 Schedule of Assessments**

Visit number	Screening	Treatment	Follow-up					
	V1	V2 Procedure	V3	V4	V5	V6	V7	V8
Weeks	-12	-	2	6	12	24	52	78
Days	Days -84 to -1	Day 1	Day 15 (+/- 3)	Day 43 (+/- 14)	Day 85 (+/- 14)	Day 169 (+/- 30)	Day 365 (+/- 30)	Day 547 (+/- 30)
Informed consent	X							
Medical History/ comorbidities	X	X						
Supplemental graft requirement confirmation	X							
Eligibility criteria verification	X	X						
Physical assessment of foot/hindfoot, vital signs	X	X	X	X	X	X	X	X
Pregnancy test [1] (if applicable)	X	X						
Standard Urinalysis [2]	X							
Clin. labs: chemistry and hematology [3]	X		X	X	X			
Immunological Testing for HBV, HCV and HIV	X							
Serum for B2A Ab testing [4]	X			X	X			
Identification of target arthrodesis site	X	X						
Subject randomization [5]		X						
Arthrodesis procedure		X						
Specific intraoperative data collection [6]		X						
Graft material volumes		X						
A/P, lateral and oblique X-rays of hindfoot/ankle	X†	X [7]		X	X	X	X	X
Foot and ankle CT scan					X	X	X	
FAAM-ADL	X				X	X	X	
Weight bearing pain at fusion site VAS	X				X	X	X	
Graft Harvest site pain VAS			X	X	X	X	X	
SF-12	X					X	X	
Adverse event evaluation [8]		X	X	X	X	X	X	X
Concomitant Medications	X	X	X	X	X	X	X	X

† At the screening/pre-operative visit, A/P, oblique and lateral X-rays will be collected (historical X-rays taken up to 24 weeks prior to the planned date of surgery will also be accepted).  
 [1] Pregnancy test may be performed within 24 hours of the procedure  
 [2] If positive for blood, leukocytes, or nitrite, microscopic urinalysis will be performed.  
 [3] HbA1c is to be performed at screening for all subjects  
 [4] B2A Antibody testing may continue past the 12 week follow-up visit if there is a positive test at 12 weeks.

[5] The subject will be randomized as close to the time of surgery as possible, with the recommendation that the randomization be performed on the day of the surgical procedure.  
 [6] See Section 6.1.4 referencing the Surgical Manual.  
 [7] Perform immediately following surgery or within 1 week following the procedure.  
 [8] Collected from time of informed consent. Post-treatment outcomes that are evaluated as efficacy endpoints, such as pain on weight-bearing, harvest site pain, etc. will not be reported as AEs.

**Table 4 Schedule of Assessments for PK Sampling**

	Screening	Treatment	Follow-up								
Visit number	V1	V2 Procedure	V3*				V4	V5	V6	V7	V8
Weeks	-12	--	2				6	12	24	52	78
Days	Days -84 to -1	Day 1	Day 2	Day 4	Day 7	Day 15	Day 43 (+/- 14)	Day 85 (+/- 14)	Day 169 (+/- 30)	Day 365 (+/- 30)	Day 547 (+/- 30)
PK assessment [1]		X	X	X	X	X					

[1] A sub-set of up to 20 evaluable AMPLEX subjects will have a PK assessment. An additional sample of blood will be collected at pre-procedure and after surgery on Days 1, 2, 4, 7, and 15.  
 \* Visit 3 will also consist of Days 2, 4 and 7, for which there will be an option for blood to be collected at home by a mobile laboratory unit.

## 7.2 Assessments Related to Endpoints

### 7.2.1 Radiographic Assessments

The collection and assessment of radiographic information will follow a pre-defined imaging core laboratory protocol. The radiographic assessments (X-ray and CT) will be read by a central core imaging laboratory. The assessments will be made by independent board-certified radiologists. The reviewers will be blinded to treatment arm and will not have access to clinical outcomes data when conducting the assessments.

More specifically, radiographic assessments of osseous bridging will be performed by two independent radiographic reviewers (the “primary reviewers”) blinded to each other’s assessments. A third independent reviewer (the “adjudicator”) will resolve disagreements between the primary reviewers. Each reviewer will be a US-based, board-certified, licensed and practicing radiologist with subspecialty training in musculoskeletal radiology.

#### 7.2.1.1 X-rays

At the screening/pre-operative visit, A/P, lateral and oblique X-rays will be collected (historical X-rays taken up to 24 weeks prior to the planned date of surgery will also be accepted). These pre-operative X-rays are the baseline for subsequent safety evaluation. After surgery A/P, oblique and lateral X-rays will be collected at the following visits: Day of Procedure (e.g., after implant or within 1 week following surgery), and 12, 24, 52 and 78 weeks post-surgery. The core imaging laboratory will provide qualitative (safety) assessments of screw loosening and radiolucencies around the screws, (new) fractures, subsidence, device migration, radiographic nonunion, osteolysis and/or heterotopic ossification in the area surrounding the implant site. A radiographic nonunion is

defined on x-ray as radiographic evidence of nonunion (as defined in the REP) and the absence of radiographic progression of healing bone (as defined in the REP). The assessment will be conducted at Weeks 52 and 78.

#### **7.2.1.2 Computerized Tomography (CT) and fusion success**

CTs will be collected at 12, 24, and 52 weeks after surgery. Radiographic CT fusion success will be determined based on evaluation of CT slices in sagittal or coronal reconstructions. A joint will be considered successfully fused if there is evidence of bridging bone over  $\geq 50\%$  of the joint. If a subject undergoes fusion at more than one site, each fusion site will be assessed independently. A subject will be considered fused if all fusion sites (full complement of joints) independently have evidence of bridging bone over at least 50% of the joint in the absence of secondary surgical or nonsurgical interventions intended to promote fusion. By definition, immediately after surgery there is 0% bridging bone in the target joint. The progression of fusion over time will be assessed in each subject by monitoring the change in fusion status from the previous visit.

#### **7.2.2 Subject self-assessments**

##### **7.2.2.1 FAAM-ADL Questionnaire**

The Foot and Ankle Ability Measure (FAAM) is a subject self-assessment questionnaire comprised of the separately scored 21-item Activities of Daily Living ADL (FAAM-ADL) and 8-item sports subscales. Each item is scored on a 5-point Likert scale anchored by 4 (no difficulty at all) and 0 (unable to do), with higher scores representing a higher levels of function.

In consideration of its target arthrodesis population, this study will utilize the FAAM-ADL sub-scale as a measure of functional improvement in the composite endpoint. The FAAM-ADL questionnaire (included in [Appendix 2](#)) will be utilized at screening and at 12, 24 and 52 weeks post-surgery. The questionnaire and its instructions for use will be provided in the SRM. Prior to administering the FAAM-ADL, subjects will be instructed on how to complete the questionnaire.

##### **7.2.2.2 Weight-bearing Pain VAS**

Weight-bearing pain at fusion site will be assessed using a VAS. Subjects will mark the location on a 100-millimeter line corresponding to the amount of pain they experienced with 0 mm being “no pain” and 100 mm being “the worst pain imaginable”. The weight-bearing pain VAS will be completed at screening and at 12, 24 and 52 weeks post procedure. The assessment and its instructions for use will be provided in the SRM.

##### **7.2.2.3 SF-12 Questionnaire**

A validated SF-12 patient questionnaire will be completed at screening and at 24 and 52 weeks post-surgery. The SF-12 Health Survey includes 12 questions from the SF-36 Health Survey. These include: 2 questions concerning physical functioning; 2 questions on role limitations because of physical health problems; 1 question on bodily pain; 1 question on general health perceptions; 1 question on vitality (energy/fatigue); 1 question on social functioning; 2 questions on role limitations because of emotional problems; and 2 questions on general mental health (psychological

distress and psychological well-being). Scoring of individual items is identical to the SF-36 Health Survey. Scoring algorithms are then applied to produce the physical component summary and mental health component summary scores. The survey and its instructions for use will be provided in the SRM.

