### *Secondary Endpoints*

- Proportion of subjects achieving CT radiographic fusion success at 12 and 24 weeks (in the absence of secondary surgical or nonsurgical interventions intended to promote fusion)
- Change from baseline in pain on weight-bearing at fusion site at 12, 24, and 52 weeks ( $\geq 20$  mm reduction from baseline on 100 mm VAS)
- ABG harvest site pain at 2, 6, 12, 24, and 52 weeks ( $< 20$  mm on 100 mm VAS)
- Change from baseline in FAAM-ADL at 12, 24, and 52 weeks
- SPC at 12 and 24 weeks
- Change from baseline in Short Form-12 (SF-12) at 24 and 52 weeks

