**SCHEDULE OF ASSESSMENTS**

	Screening	Treatment	Follow-up					
Visit number	V1	V2 Procedure	V3	V4	V5	V6	V7	V8
Weeks	-12	--	2	6	12	24	52	78
Days	Days -84 to -1	Day 1	Day 15 (+/- 3)	Day 43 (+/- 14)	Day 85 (+/- 14)	Day 169 (+/- 30)	Day 365 (+/- 30)	Day 547 (+/- 30)
Informed consent	X							
Medical History/ comorbidities	X	X						
Supplemental graft requirement confirmation	X							
Eligibility criteria verification	X	X						
Physical assessment of foot/hindfoot, vital signs	X	X	X	X	X	X	X	X
Pregnancy test [1] (if applicable)	X	X						
Standard Urinalysis [2]	X							
Clin. labs: chemistry and hematology [3]	X		X	X	X			
Immunological Testing for HBV, HCV and HIV	X							
Serum for B2A Ab testing [4]	X			X	X			
Identification of target arthrodesis site	X	X						
Subject randomization [5]		X						
Arthrodesis procedure		X						
Specific intraoperative data collection [6]		X						
Graft material volumes		X						
A/P, lateral and oblique X-rays of hindfoot/ankle	X†	X [7]		X	X	X	X	X
Foot and ankle CT scan					X	X	X	
FAAM-ADL	X				X	X	X	
Weight bearing pain at fusion site VAS	X				X	X	X	

Graft Harvest site pain VAS			X	X	X	X	X	
SF-12	X						X	X
Adverse event evaluation [8]		X	X	X	X	X	X	X
Concomitant Medications	X	X	X	X	X	X	X	X

† At the screening/pre-operative visit, A/P, oblique and lateral X-rays will be collected (historical X-rays taken up to 24 weeks prior to the planned date of surgery will also be accepted).  
 [1] Pregnancy test may be performed within 24 hours of the procedure.  
 [2] If positive for blood, leukocytes, or nitrite, microscopic urinalysis will be performed.  
 [3] HbA1c is to be performed at screening for all subjects.  
 [4] B2A Antibody testing may continue past the 12 week follow-up visit if there is a positive test at 12 weeks.  
 [5] The subject will be randomized as close to the time of surgery as possible, with the recommendation that the randomization be performed on the day of the surgical procedure.  
 [6] See Section 6.1.4 referencing the Surgical Manual.  
 [7] Perform immediately following surgery or within 1 week following the procedure.  
 [8] Collected from time of informed consent. Post-treatment outcomes that are evaluated as efficacy endpoints, such as pain on weight-bearing, harvest site pain, etc. will not be reported as AEs

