9.1 General Considerations

Non-inferiority tests will be conducted at a one-sided 5% significance level whereas superiority tests will be conducted at a two-sided 5% significance level per an agreement with the FDA in the AMPLEX IDE.

All efficacy analyses will be conducted for the mITT analysis set unless specified otherwise. The primary and key secondary efficacy endpoints will be analyzed by a fixed-sequence procedure according to the following order to maintain the overall Type 1 error rate to a one-sided 5% for non-inferiority and a two-sided 5% for superiority testing.

- 1) Non-inferiority of AMPLEX to ABG in the primary efficacy endpoint (primary analysis)
- 2) Non-inferiority of AMPLEX to ABG in the key secondary efficacy endpoint
- 3) Superiority of AMPLEX to ABG in the key secondary efficacy endpoint
- 4) Superiority of AMPLEX to ABG in the primary efficacy endpoint

Testing procedure will begin with the non-inferiority test for the primary efficacy endpoint, and each test will be conducted without adjustment of multiplicity as long as all preceding tests are significant. All other secondary endpoints will be presented with the point estimate of the treatment group difference and the corresponding 2-sided 90% and 95% confidence intervals.

For visit-based data, the data collected on the day that is closest to the scheduled trial day within a window specified in Table 1 will be assigned to the corresponding analysis visit. If the closest day cannot be uniquely identified for an analysis visit, the data collected on an earlier trial day will be assigned to the analysis visit. Visit windows for the analysis are specified in a way to utilize all collected data as much as possible and are different from the protocol specified visit windows.

Table 1 Scheduled trial day and window for analysis visits

Analysis visit	Scheduled trial day	Analysis window
Baseline	Day -84 to Day 1	Up to prior to the initiation of surgery
Post-Operative CT and X-ray	Day 1	Day 1 to Day 29
Week 2	Day 15	Day 2 to Day 29
Week 6	Day 43	Day 30 to Day 64
Week 12	Day 85	Day 65 to Day 127
Week 24	Day 169	Day 128 to Day 267
Week 52	Day 365	Day 268 to Day 456
Week 78	Day 547	Day 457 to Day 637

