The change from baseline in SF-12 scores (PCS and MCS) at 24 and 52 weeks will be analyzed by the repeated measures ANCOVA using the similar ANCOVA models described for FAAM-ADL. Each score will be calculated based on the algorithm to be provided by the licensee.

The FAAM-ADL score will be calculated based on the algorithm described in [Appendix 2](#).

10 Safety

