10.5 Anti-B2A Antibody

Numbers and percentages of subjects with anti-B2A antibodies at screening, 6 weeks, and 12 weeks will be summarized. If a subject had a positive test at 12 weeks, subsequent test results will be presented in a listing.

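### The synopsis schedule places SF-12 at Weeks 52 and 78 instead of 24 and 52, and SAP Table 1 leaves a protocol-compliant Day 29 visit outside Week 6

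*Protocol*

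**What the plan says.** **SF-12.** The synopsis lists the secondary endpoint as "Change from baseline in Short Form-12 (SF-12) at 24 and 52 weeks", and Protocol 2.2.2 and SAP 2.2.3 repeat it. Protocol 7.2.2.3 sets collection to match: "A validated SF-12 patient questionnaire will be completed at screening and at 24 and 52 weeks post-surgery". The Week 24 procedures (Protocol 6.1.9) instruct the site: "Review the instructions for and ask the subject to complete the SF-12 Questionnaire". Section 6.1.10 does the same at Week 52, and Section 6.1.11 (Week 78) lists no SF-12. Protocol Table 3 and SAP Appendix 3 mark V1, V6 and V7. SAP 9.3.2 says: "The change from baseline in SF-12 scores (PCS and MCS) at 24 and 52 weeks will be analyzed by the repeated measures ANCOVA". The exception is the synopsis table headed "SCHEDULE OF ASSESSMENTS", where the SF-12 marks stand under V1, V7 (Week 52) and V8 (Week 78), with nothing under V6 (Week 24).

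**Week 6 window.** Protocol 6.1.7 and Table 3 set the Week 6 visit at Day 43 with a tolerance of 14 days either side. SAP 9.1 gives the rule for mapping records to analysis visits: "the data collected on the day that is closest to the scheduled trial day within a window specified in Table 1 will be assigned". Its Table 1 ends Week 2 at Day 29 and gives Week 6 as "Day 30 to Day 64". The same section explains that the analysis windows differ from the protocol's on purpose, so that as many collected records as possible are used. SAP 10.5 adds: "Numbers and percentages of subjects with anti-B2A antibodies at screening, 6 weeks, and 12 weeks will be summarized".

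**The concern.** The protocol carries two schedules of assessments that disagree on when a listed secondary endpoint is measured. A site that followed the synopsis version would have no Week 24 SF-12. That is one of only two post-baseline points in the model, and a self-report for Week 24 cannot be collected afterwards. The Week 78 form gathered in its place enters no planned analysis.

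The window table raises a separate and smaller problem. A subject seen on the first permitted day of the Week 6 visit has complied with the protocol, yet the SAP does not count that visit as Week 6. Harvest-site pain at Week 6 (a secondary endpoint) and anti-B2A antibody at Week 6 (a safety endpoint) would then appear as missing although they were collected. That runs against the SAP's own reason for having separate analysis windows.

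**Working it through.** **SF-12 row.** Both protocol tables have eight visit columns, V1 to V8.

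- Synopsis schedule: eight cells, marks at V1, V7, V8.
- Table 3: marks at V1, V6, V7.
- The synopsis FAAM-ADL row, read the same way, gives V1, V5, V6, V7, as the text requires, so the column count is sound.
- A Week 78 form cannot stand in for Week 24. The SAP windows are Day 128–267 for Week 24 and Day 457–637 for Week 78.

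**SAP window limits.** The scheduled days are 15, 43, 85, 169, 365 and 547. The midpoints between neighbours are:

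- (15 + 43)/2 = 29
- (43 + 85)/2 = 64
- (85 + 169)/2 = 127
- (169 + 365)/2 = 267
- (365 + 547)/2 = 456

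These reproduce the upper limits in SAP Table 1 for Weeks 2 to 52 exactly. The rule is therefore the midpoint, with the midpoint day given to the earlier visit.

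**Protocol window against SAP window**

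| Visit | Protocol days | SAP days | Compliant days outside |
|---|---|---|---|
| Week 2 | 12–18 | 2–29 | none |
| Week 6 | 29–57 | 30–64 | Day 29 |
| Week 12 | 71–99 | 65–127 | none |
| Week 24 | 139–199 | 128–267 | none |
| Week 52 | 335–395 | 268–456 | none |
| Week 78 | 517–577 | 457–637 | none |

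Day 29 is the only compliant follow-up day that misses its own analysis visit. It is 14 days from both Day 15 and Day 43.

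**What happens to a Day 29 record**

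- Harvest-site VAS, laboratory values and vital signs: with an on-time Week 2 visit, the record nearer Day 15 is chosen for Week 2, and the Day 29 record belongs to no analysis visit. Without a Week 2 record, the Day 29 value is reported as Week 2.
- Antibody: no sample is scheduled at Week 2, so the Day 29 result is assigned there, and SAP 10.5 does not summarise that visit.
- X-ray: Day 29 also falls in the Post-Operative CT and X-ray window (Day 1–29), so the film is not counted at Week 6.
- Laboratory values still reach the table of any post-baseline markedly abnormal liver test (SAP 10.6.3) and the full listing (SAP 10.6.4).

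**Size.** The Week 6 window holds 57 − 29 + 1 = 29 days. Assuming an even spread of visits, the share on Day 29 is 1/29 = 3.4%.

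- ABG harvest-site pain: 160/29 = 5.5, or about 5 to 6 subjects.
- AMPLEX antibody: 320/29 = 11.0, or about 11 subjects.

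**The case against.** On SF-12, the case against is that this is a clerical slip in a summary table. The reading rests on cell positions in text extracted from a PDF, and the row sits after a break in the table. The correct timing is given in many other places, and Protocol 4.2.1 sends readers to Section 6 for the evaluations at each visit. Most of this stands. The row has its full eight cells and the rows around it align, so a real misplacement is likely, but the original page should be checked. A reader might infer that a whole site's Week 24 data would be lost. That would require the site to ignore both Section 6.1.9 and Table 3, and nothing in the documents suggests it would.

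On Day 29, the case against is that the SAP applies one midpoint convention throughout, says openly that its windows differ from the protocol's, and had to give an equidistant day to one side or the other. That explains how the limit arose. It does not explain a limit that excludes a compliant visit when the stated aim is to use more data.

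Two stronger readings are tempting and fail. One is that Day 29 laboratory values go unused: they do not, because SAP 10.6.3 and 10.6.4 are not tied to a visit. The other is that about 16 subjects (480/29 = 16.6) could lose harvest-site pain data: that measure is collected in the ABG group only (Protocol 7.2.2.4), so 160 is the right base. Nor is the even-spread figure an upper bound, since it is only an assumption about visit timing.

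The antibody effect is also limited. Week 12 is still sampled and summarised, and Protocol 7.3.4 requires further sampling after a positive result whatever the analysis window.

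**Conclusion.** Both points hold, and both are minor.

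- The synopsis SF-12 row contradicts every other statement of the SF-12 timing in the two documents. The potential loss at a site following it is one of two analysed post-baseline points on a secondary endpoint without multiplicity adjustment. The likelihood is low because the operative text is correct. The finding is subject to a look at the original page.
- A compliant Day 29 visit is lost from the by-visit Week 6 summaries of harvest-site pain (ABG only), antibody, laboratory values, vital signs and X-ray. Under an even spread this is about 5 to 6 of 160 ABG subjects for harvest-site pain and about 11 of 320 AMPLEX subjects for antibody. Visits clustering near Day 43 would make it fewer.

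The second point assumes that Table 1, which stands in the SAP's efficacy section, also governs the by-visit safety summaries. Its Week 78 row supports this, since no efficacy assessment is scheduled at that visit in Table 3 or SAP Appendix 3, and the SAP's safety section gives no other windows.

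The Week 52 primary endpoint, the Week 52 key secondary endpoint and the sample size are untouched.

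**What to change.** 1. In the protocol synopsis schedule, after checking the original page, place the SF-12 marks at V1, V6 and V7, as in Table 3. This is one table row.
2. In SAP Table 1, set Week 2 to Day 2–28, Week 6 to Day 29–64, and Post-Operative CT and X-ray to Day 1–28. Every protocol-compliant follow-up visit then falls in its own analysis window.

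The second change has a small cost. It departs from the uniform midpoint convention at one boundary, and a Week 2 visit held as late as Day 29 would be assigned to Week 6. Such a visit is already 29 − 18 = 11 days outside the protocol's Week 2 window.
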